Safety analyses will be performed separately within both phases of the study and for all patients combined. Data from all patients that receive at least one dose of FPA150 monotherapy or part of one dose of either pembrolizumab or FPA150 in the combination cohort will be included in the safety analyses. AEs, clinical laboratory information, vital signs, ECOG performance status, weight, ECGs, and concomitant medications/procedures will be tabulated and summarized. In addition, the incidence of DLTs in Phase 1a will be summarized.

Efficacy Analysis:

The ORR will be summarized with frequencies and percentages with 90% confidence interval (CI). The duration of response (DOR) for complete response (CR) and partial response (PR) patients for all treated patients will be summarized with descriptive statistics (N, arithmetic mean, standard deviation (SD), median, minimum, and maximum). The ORR, DOR, and PFS will be determined using RECIST v1.1. Kaplan-Meier methodology will be used to estimate median DOR and PFS and corresponding 95% CI. A 2-stage design will be used to determine the actual enrolled subjects. Sponsor will evaluate efficacy in phase 1b on an ongoing basis and may suspend or terminate enrollment in specific cohorts if ≤ 1 response (CR or PR per RECIST 1.1) is observed in the first 16 patients enrolled in each cohort. In this case, the probability of early termination is 0.81 with 0.05 responder rate for futility and 0.2 responder rate for efficacy.

Pharmacokinetic Analysis:

Individual and mean (\pm SD) serum FPA150 concentration-time data from monotherapy will be tabulated and plotted by dose level/cohort. PK parameters will be tabulated and summarized by dose level/cohort when appropriate and applicable. The impact of immunogenicity on FPA150 exposure will be assessed, tabulated, and summarized by dose level as data allow.

For cohorts of FPA150 in combination with pembrolizumab samples for PK analysis will be collected and held. Individual and mean (\pm SD) serum concentration-time data for FPA150 and pembrolizumab may be tabulated and plotted by dose level/cohort. PK parameters for the combination may be tabulated and summarized by dose level/cohort when appropriate and applicable.

Immunogenicity Analysis:

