9.1 Sample Size Determination

For Phase 1a, this study is designed as a dose escalation study with objectives that include determination of an MTD and/or RD for FPA150 monotherapy and FPA150 combined with pembrolizumab. It will also include assessments of the safety and tolerability of FPA150 monotherapy and in combination with pembrolizumab. The sample size of this study was not determined by strict statistical considerations. The total number of patients planned for this study is estimated to be up to 278.

Phase 1a will enroll up to 68 patients. The 68 patients include 23 to 26 patients in the Phase 1a Monotherapy Dose Escalation cohorts, 6 to 22 patients in the Phase 1a Combination Safety Lead-in cohort and up to 20 additional patients in the Phase 1a Monotherapy Dose Exploration cohorts to further evaluate safety, PK, pharmacodynamics, and clinical activity at 1 or more dose levels (to be conditional upon the dose level clearing DLT criteria).

For the objective of estimating the ORR of FPA150 in the Phase 1b Monotherapy and Combination Dose Expansion cohorts, it is estimated that up to 30 patients will be enrolled to ensure 25 evaluable patients in each cohort. The following table displays the corresponding 2-sided 90% confidence interval (CI) and the precision for the various observed response rates based on 25 evaluable patients. The sample size of 25 is chosen to ensure that it will allow to exclude 10% when the observed ORR is 24% or higher ([Agresti 1998](#)).

Phase 1b will enroll up to 210 patients with specific tumor types. Up to 30 patients are planned for each of the 3 FPA150 Monotherapy Dose Expansion cohorts, and one additional cohort of FPA150 in combination with pembrolizumab. Additional cohorts of up to 30 patients each may be enrolled, based on emerging clinical and translational data.

Table 11: Two-Sided 90% Confidence Intervals of the Observed Response Rates

Sample Size	Observed Response Rate	90% CI	Precision (longest one-sided CI length*)
25	5/25 (20%)	(8%, 38%)	18%
	6/25 (24%)	(11%, 42%)	18%
	7/25 (28%)	(14%, 46%)	18%
	8/25 (32%)	(17%, 50%)	18%
	9/25 (36%)	(20%, 54%)	18%
	10/25 (40%)	(24%, 58%)	18%

Abbreviations: CI = confidence interval.

*Distance from the observed response rate to the lower or upper CI boundary.

Considering it is possible to open successive cohorts after data is reviewed, up to 210 patients may be enrolled in Phase 1b (not to exceed 30 patients in any individual cohort).

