9.4.2 Efficacy Analyses

The ORR will be summarized with frequencies and percentages with 90% CI by each dose/cohort. The duration of response (DOR) for complete response (CR) and partial response (PR) patients and PFS for all treated patients will be summarized with descriptive statistics (N, arithmetic mean, SD, median, minimum, and maximum). The ORR, DOR, and PFS will

be determined using RECIST v1.1. Kaplan-Meier methodology will be used to estimate median DOR and PFS and corresponding 95% CI.

ORR, DOR, and PFS are defined below.

ORR: defined as the total number of patients with confirmed responses of either CR or PR per RECIST v1.1 divided by the total number of patients who are evaluable for a response.

DOR: defined as the time from onset of response (CR or PR) that is subsequently confirmed to the first observation of progressive disease or death due to any cause. Patients who are alive and progression-free at the time of data analysis will be censored at the time of their last assessment for tumor response.

PFS: defined as the time from the patient's first dose to the first observation of progressive disease or death due to any cause. Patients who are alive and progression-free at the time of data analysis will be censored at the time of their last assessment for tumor response.

More details of censoring rule for DOR and PFS will be outlined in SAP.

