1.3 Sample Size

For Phase 1a, this study is designed as a dose escalation study with objectives that include determination of an MTD and/or RD for FPA150 monotherapy and FPA150 combined with pembrolizumab. It will also include assessments of the safety and tolerability of FPA150 monotherapy and in combination with pembrolizumab. The sample size of this study was not determined by strict statistical considerations. The total number of patients planned for this study is estimated to be up to 278.

Phase 1a will enroll up to 68 patients. The 68 patients include 23 to 26 patients in the Phase 1a Monotherapy Dose Escalation cohorts, 6 to 22 patients in the Phase 1a Combination Safety Lead-in cohort and up to 20 additional patients in the Phase 1a Monotherapy Dose Exploration cohorts to further evaluate safety, PK, pharmacodynamics, and clinical activity at 1 or more dose levels (to be conditional upon the dose level clearing DLT criteria).

For the objective of estimating the ORR of FPA150 in the Phase 1b Monotherapy and Combination Dose Expansion cohorts, it is estimated that up to 30 patients will be enrolled to ensure 25 evaluable patients in each cohort. The following table displays the corresponding 2-sided 90% confidence interval (CI) and the precision for the various observed response rates based on 25 evaluable patients. The sample size of 25 is chosen to ensure that it will allow to

exclude 10% when the observed ORR is 24% or higher (Agresti 1998).

Phase 1b will enroll up to 210 patients with specific tumor types. Up to 30 patients are planned for each of the 3 FPA150 Monotherapy Dose Expansion cohorts, and one additional cohort of FPA150 in combination with pembrolizumab. Additional cohorts of up to 30 patients each may be enrolled, based on emerging clinical and translational data.

Table 7: Two-Sided 90% Confidence Intervals of the Observed Response Rates

Sample Size	Observed Response Rate	90% CI	Precision (longest one-sided CI length*)
25	5/25 (20%)	(8%, 38%)	18%
	6/25 (24%)	(11%, 42%)	18%
	7/25 (28%)	(14%, 46%)	18%
	8/25 (32%)	(17%, 50%)	18%
	9/25 (36%)	(20%, 54%)	18%
	10/25 (40%)	(24%, 58%)	18%

Abbreviations: CI = confidence interval.

*Distance from the observed response rate to the lower or upper CI boundary.

Considering it is possible to open successive cohorts after data is reviewed, up to 210 patients may be enrolled in Phase 1b (not to exceed 30 patients in any individual cohort).

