3.4 Multiple Comparisons

Adjustments for multiplicity will not be made, because no formal statistical testing will be performed in this study.

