6.1 Objective Response Rate

ORR is defined as the proportion of subjects who achieve best overall response (BOR) of either complete response (CR) or partial response (PR) based on investigator assessment tumor lesions per RECIST v1.1. The BOR is the best response documented from first dose until the end of study, first disease progression, death, or start of new anti-cancer therapy, whichever is earlier. Subjects, who do not have sufficient baseline or on-study tumor status information to be adequately assessed for response status (i.e., those with BOR of not evaluable [NE]), or received anticancer therapy other than the study treatment, will be considered as non-responders and will be included in the denominators in calculations of response rates.

When the date of initiation of new anticancer therapy other than the study treatment is incomplete or missing, the following algorithm will be followed:

- If the day is missing but the month and year are available, then the imputed day will be the last day of the month.
- If day and month are missing but year is available, then the imputed day and month will be the last day of the month for the last adequate disease assessment if they have the same year.

The analysis of ORR will be performed based on the Efficacy-Evaluable Analysis Set. ORR with corresponding 2-sided 95% CI based on Clopper-Pearson method along with each category of BOR will be summarized by treatment group. Patients who don't have any postbaseline adequate tumor assessments will be counted as non-responders.

By-subject listings will be provided for target lesion, nontarget lesion, new lesion, and investigator-assessed timepoint response. A by-subject listing of new anticancer therapy will also be provided.

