6.3 Changes from Protocol-Specified Efficacy Analysis

Analysis and summary will not be provided for time to duration of response and progression-free

survival due to limitation of the data.

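### SAP 6.1 reports ORR with a 95% CI where the protocol specifies 90% and SAP 1.3 sizes on 90%, and SAP 6.3 does not declare it; at 25 evaluable patients the threshold for excluding 10% moves from 6/25 (24%) to 7/25 (28%)

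*SAP*

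**What the plan says.** - **Protocol 9.4.2:** "The ORR will be summarized with frequencies and percentages with 90% CI by each dose/cohort". The synopsis gives the same level. In these sections the protocol uses 95% only for the Kaplan-Meier medians of duration of response (DOR) and progression-free survival (PFS).
- **Protocol 9.1:** "The sample size of 25 is chosen to ensure that it will allow to exclude 10% when the observed ORR is 24% or higher". The supporting table is built on two-sided 90% limits.
- **SAP 1.3** repeats that argument. Its Table 7 is headed "Two-Sided 90% Confidence Intervals of the Observed Response Rates", and the text again says that 25 patients "exclude 10% when the observed ORR is 24% or higher".
- **SAP 6.1** sets the analysis to be reported: "ORR with corresponding 2-sided 95% CI based on Clopper-Pearson method along with each category of BOR will be summarized by treatment group".
- **SAP 6.3**, headed as the changes from the protocol's efficacy analysis, has one entry: "Analysis and summary will not be provided for time to duration of response and progression-free" survival. The ORR interval is not mentioned.
- **SAP 3.4:** "Adjustments for multiplicity will not be made, because no formal statistical testing will be performed in this study".

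On display, SAP 3 lists Phase 1b monotherapy as one summary group. SAP 3.2 groups by treatment actually received and combines the combination lead-in with the Phase 1b combination cohort. Neither section says whether cohorts 1b1, 1b2 and 1b3 get separate ORR results.

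**The concern.** The interval that justified the cohort size is not the interval that will be reported. With no formal test, the confidence interval is the main inferential statement about ORR, and the choice of 25 rests on its lower limit at 24%. A reader who takes SAP 1.3 at its word and sees 6 responders in 25 expects 10% to be excluded; the ORR table will show a lower limit below 10%. Because SAP 6.3 is silent, the same reader would also assume that the ORR analysis follows the protocol.

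A secondary matter is display. The 25 patients and the 90% interval were set for each cohort. If Phase 1b monotherapy were shown only as one group, or the combination cohort only pooled with its lead-in, a reader could not recover the cohort-level interval from the reported counts. Protocol 9.3 allows both cohort and overall summaries, so a pooled row is acceptable as an addition. What the SAP leaves unsaid is that it does not replace the cohort result.

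**Working it through.** **Inputs.** n = 25 evaluable per cohort, reference rate 10% and threshold 24% (protocol 9.1, SAP 1.3); level 90% (protocol synopsis, 9.1 and 9.4.2; SAP 1.3) or 95% (SAP 6.1); Clopper-Pearson method (SAP 6.1).

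**Formula.** For x responders in n and level 1 − α, the lower limit is the α/2 quantile of Beta(x, n − x + 1) and the upper limit is the 1 − α/2 quantile of Beta(x + 1, n − x).

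**Steps 1 and 2: reproduce the plan's table at 90%, then change only the level.** The last two columns give the distance from the observed rate to the farther limit, in percentage points.

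| Responders | 90% limits | 95% limits | Farther side, 90% | Farther side, 95% |
|---|---|---|---|---|
| 5/25 (20%) | 8.2–37.5 | 6.8–40.7 | 17.5 | 20.7 |
| 6/25 (24%) | 11.0–42.0 | 9.4–45.1 | 18.0 | 21.1 |
| 7/25 (28%) | 13.9–46.2 | 12.1–49.4 | 18.2 | 21.4 |
| 8/25 (32%) | 17.0–50.4 | 15.0–53.5 | 18.4 | 21.5 |
| 9/25 (36%) | 20.2–54.4 | 18.0–57.5 | 18.4 | 21.5 |
| 10/25 (40%) | 23.6–58.3 | 21.1–61.3 | 18.3 | 21.3 |

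The 90% columns match all six printed rows and the printed precision of 18. The sizing text cites a paper on approximate intervals, but the table is not Agresti-Coull: at 5/25 that method gives about 10% to 36% at 90%, against the printed 8% to 38%. SAP 6.1 therefore keeps the table's method and changes its level.

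**Step 3: check the threshold through exact tails.** A Clopper-Pearson lower limit exceeds 10% when P(X ≥ x | n = 25, p = 0.10) is below α/2.
- P(X ≥ 6) = 0.0334: below 0.05 (90% interval), above 0.025 (95% interval).
- P(X ≥ 7) = 0.0095: below both.

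So the smallest count that excludes 10% is 6 at 90% and 7 at 95%.

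**Step 4: other evaluable numbers.** Smallest count whose lower limit exceeds 10%:

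| Evaluable n | 90% | 95% |
|---|---|---|
| 16–17 | 5 | 5 |
| 18–20 | 5 | 6 |
| 21–23 | 6 | 6 |
| 24–27 | 6 | 7 |
| 28–29 | 7 | 7 |
| 30–34 | 7 | 8 |
| 35–36 | 8 | 8 |
| 37–40 | 8 | 9 |

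Both the planned 25 and the enrolment cap of 30 fall where the count rises by one. The pooled combination group could reach 30 + 10 = 40, assuming that the cohort and the lead-in both fill, at one dose, and all patients are evaluable. There 8/40 has a lower limit of 10.4% at 90% and 9.1% at 95%, and 9/40 has 10.8% at 95%.

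**Step 5: futility rule.** P(X ≤ 1 | n = 16, p = 0.05) = 0.811, which agrees with the stated 0.81 and does not involve the confidence level.

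**The case against.** The strongest reply is that little depends on this. ORR is secondary in Phase 1b and exploratory in Phase 1a, all analyses are descriptive, and both documents say that the sample size was not set on strict statistical grounds. No decision rule uses exclusion of 10%. The only operating rule, at most 1 response in the first 16, ignores the interval. A 95% interval is wider, so it cannot flatter the drug, and anyone with the counts can recompute 90%. This stands, and it limits the weight of the point.

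Second, protocol 9 allows deviations from planned analyses to be justified in the final study report, and protocol 9.3 requires an amendment only when a principal feature changes. That is a legitimate later route. It does not explain why the SAP's own list of changes omits this one, or why SAP 1.3 and 6.1 differ within one document.

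Third, the move to 28% is specific to 25 evaluable patients and to Clopper-Pearson. Some cohort sizes show no change in the required count. Under 95% Wilson or Agresti-Coull limits, 6/25 would still exclude 10% (lower limits 11.5% and 11.2%). That is correct, but 25 is the plan's own number and Clopper-Pearson is the method that SAP 6.1 names and the table uses.

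Fourth, the display point is inferred from silence: the SAP never says that the three monotherapy cohorts will be pooled for ORR. That is fair, and it is why the point is secondary.

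**Conclusion.** The concern holds. SAP 6.1 departs from the protocol's 90% level and from the SAP's own sizing basis without declaring it. SAP 1.3 remains correct for a 90% interval but not for the one to be reported. At n = 25 with Clopper-Pearson limits, the cost is one responder (6 to 7, or 24% to 28%) and about 3 points of precision (17.5–18.4 becomes 20.7–21.5). At other evaluable numbers the required count rises by one or stays the same; the documents do not give the actual evaluable numbers.

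It should be fixed because the plan is wrong as written and the correction is nearly free. It does not threaten a trial conclusion: there is no type I error claim and the stopping rule is untouched. Confidence is high on the interval level, which alone carries the rating. It is moderate on the display point, where the SAP gives a grouping rule but does not say whether the tumour cohorts appear separately.

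**What to change.** **Preferred.** In SAP 6.1, state that ORR is reported with a two-sided 90% Clopper-Pearson interval, by dose level in Phase 1a and separately for cohorts 1b1, 1b2, 1b3 and 1bC1. Label a 95% interval and the pooled lead-in plus 1bC1 result as supplementary. Confine this to the ORR table and leave the SAP 3.2 grouping as it is elsewhere. The cost is one passage and separate cohort columns in one table, with no new data and no change to disposition, exposure or safety tables.

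**Alternative.** If 95% is to be the main interval, declare and justify it in SAP 6.3, restate SAP 1.3 so that 10% is excluded when at least 7/25 (28%) respond, and recompute Table 7 at 95%. The cost is one line, one sentence and one table, plus the higher stated threshold. The statement that each Phase 1b cohort is shown separately is still needed in this case.

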3.1.2 Efficacy-Evaluable Analysis Set

The Efficacy-Evaluable Analysis Set includes all subjects received at least 1 dose of FPA150, had at least 1 postbaseline evaluable tumor assessment unless death or clinical progressive disease occurred prior to the first post baseline disease assessment.

The Efficacy-Evaluable Analysis Set will be used in the summary of efficacy data.

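### SAP 3.1.2 and 6.1 do not agree on treated patients who have no evaluable post-baseline scan and neither died nor clinically progressed first; leaving them out can only raise ORR or leave it unchanged

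*SAP*

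**What the plan says.** SAP 3.1.2 admits to the Efficacy-Evaluable Analysis Set a subject who received at least one dose and "had at least 1 postbaseline evaluable tumor assessment unless death or clinical progressive disease occurred prior to the first post baseline disease assessment". SAP 6.1 then fixes the set for response rate: "The analysis of ORR will be performed based on the Efficacy-Evaluable Analysis Set".

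SAP 6.1 also holds two non-responder rules. Subjects whose best overall response is not evaluable, or who received other anticancer therapy, "will be considered as non-responders and will be included in the denominators in calculations of response rates". At the end of the analysis paragraph it adds that patients who lack "any postbaseline adequate tumor assessments will be counted as non-responders". Neither sentence is limited to members of the efficacy-evaluable set.

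Protocol 9.4.2 defines ORR as confirmed responders "divided by the total number of patients who are evaluable for a response". Protocol 9.1 plans that "up to 30 patients will be enrolled to ensure 25 evaluable patients in each cohort", and SAP 1.3 repeats this. The stated purpose of 25 evaluable patients is to "exclude 10% when the observed ORR is 24% or higher", judged on two-sided 90% intervals.

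**The concern.** Take a patient who is dosed and then withdraws consent, stops for toxicity or starts another therapy before any evaluable scan. SAP 3.1.2 takes this patient out of the ORR set. SAP 6.1, read as written, counts the same patient as a non-responder. Nothing says which rule prevails, so two programmers could obtain two response rates from the same data.

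The choice is not neutral. Exclusion depends on what happened after dosing, and it removes only patients who could not have been recorded as responders. The cohorts are open-label, investigator-assessed and uncontrolled, so no comparison group offsets the shift. ORR also carries more weight than the protocol intended: SAP 6.3 drops duration of response and progression-free survival, and SAP section 6 contains no overall survival analysis. ORR is thus the only efficacy endpoint the SAP summarises.

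**Working it through.** **1. Who is affected.** Treated patients, with the two SAP sections side by side:

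| Patient | SAP 3.1.2 | SAP 6.1 | Agree? |
|---|---|---|---|
| Evaluable post-baseline scan | in set | classified by best response | yes |
| Death or clinical progression before first assessment | in set (exception) | non-responder | yes |
| No evaluable scan for any other reason | out of set | non-responder | no |

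Only the third row is in conflict. The protocol's evaluable population (9.2) also requires eligibility and measurable baseline lesions. SAP 3.1.2 drops both requirements, so under the SAP the third row is everyone who was dosed but left out of ORR.

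**2. Direction.** Let r be the responders, n the patients in the set, and m the omitted patients. None of the m can be a responder, so the two candidate rates are r/n and r/(n + m). Since r/n ≥ r/(n + m), omission raises ORR or, when r = 0 or m = 0, leaves it unchanged.

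**3. Reproducing the plan's interval.** The Clopper-Pearson limits for r of n at level 1 − α are

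- L = Beta quantile(α/2; r, n − r + 1)
- U = Beta quantile(1 − α/2; r + 1, n − r)

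For 6/25 with α = 0.10, L = Beta(0.05; 6, 20) = 11.0% and U = Beta(0.95; 7, 19) = 42.0%. This matches the (11%, 42%) in SAP Table 7 and protocol Table 11, and the other rows (5/25 to 10/25) also reproduce. Wilson limits (13.0%, 40.1%) and Agresti-Coull limits (12.7%, 40.3%) do not match the 6/25 row.

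**4. Adding omitted patients back.** Neither document states m. I assume a range of 0 to 5, because 30 (the ceiling) − 25 (evaluable) = 5. With 25 in the set and r = 6:

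| m | r/(n + m) | ORR | 90% lower bound |
|---|---|---|---|
| 0 | 6/25 | 24.0% | 11.0% |
| 1 | 6/26 | 23.1% | 10.6% |
| 2 | 6/27 | 22.2% | 10.1% |
| 3 | 6/28 | 21.4% | 9.8% |
| 4 | 6/29 | 20.7% | 9.4% |
| 5 | 6/30 | 20.0% | 9.1% |

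At m = 5 the full 90% interval is 9.1% to 35.7%. The lower bound crosses 10% between m = 2 and m = 3.

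**5. The same check at the 95% level in SAP 6.1** (α = 0.05):

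- 6/25: 9.4% to 45.1%. This does not exclude 10%, whatever the denominator.
- 7 responses: lower bound 12.1% at 7/25, 10.3% at 7/29 and 9.9% at 7/30. The exclusion is lost only if all five are added back.

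**The case against.** The strongest reply is that the sections can be read together. In SAP 6.1 the non-responder sentence follows the naming of the efficacy-evaluable set, so it may govern only patients inside that set: early deaths, early clinical progressions and not-evaluable best responses. On that reading both non-responder rules have real content. This stands as a possible reading, and it rules out calling the sections contradictory for every patient without a scan. It does not settle the residual group, because the sentence carries no such limit.

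Procedures should also keep the group small. Protocol 8.6.1 asks for scans at the end-of-treatment visits when a patient stops before a scheduled scan, and continues assessments about every 12 weeks after stopping for reasons other than progression, consent withdrawal or new therapy. Many toxicity discontinuations should therefore yield a scan. That lowers the likely count but does not say how the remaining patients are handled.

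Two stronger conclusions are tempting and not supported:

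- A reader might infer that the plan expects five patients without scans in each cohort. The text allows up to 30 enrolled to secure 25 evaluable and gives no reasons. The protocol's evaluable definition has other criteria, so a non-evaluable patient need not be one with a missing scan.
- A reader might infer that the denominator reverses the exclusion of 10%. At 90% with 6 responses this needs at least 3 omitted patients; with 0 to 2 the exclusion stands. At the SAP's 95% level nothing is reversed at 6/25, because 10% is not excluded there to begin with. That follows from the 90% versus 95% difference between protocol 9.4.2 and SAP 6.1, not from the denominator.

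The stakes are also bounded. ORR is secondary in Phase 1b, the 10% statement is a precision target, SAP 3.4 says there is no formal testing, and the two-stage rule counts the first 16 patients enrolled, so it does not depend on this denominator. By-subject listings on the Safety Analysis Set would let a careful reader recompute an all-treated rate.

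**Conclusion.** The point holds for a defined residual group: treated patients with no evaluable post-baseline scan who neither died nor clinically progressed before the first assessment. For them SAP 3.1.2 and 6.1 give different handling and no text decides between them. Following 3.1.2 can only raise ORR or leave it unchanged.

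The size is conditional. With 6 responses, 25 patients in the set and an assumed 0 to 5 omitted, the difference is at most 4 percentage points (24% against 20%). The 90% lower bound drops below 10% from 3 omitted patients upward. At 95%, the only loss of the exclusion among the 6- and 7-response cases checked is 7 responses with all five added back. The point merits correction because ORR is the sole summarised efficacy endpoint and the remedy is cheap; no decision rule in the plan is shown to be compromised.

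**What to change.** In SAP 6.1, apply the non-responder rule to all treated Phase 1b patients, using the Safety Analysis Set already defined in SAP 3.1.1, and report that ORR with its CI beside the efficacy-evaluable ORR. Reword 3.1.2 or 6.1 so that each patient without a scan has one stated handling in each row. For example, limit the existing 6.1 sentence to members of the efficacy-evaluable set, and state that in the all-treated row every dosed patient without an adequate post-baseline assessment is a non-responder.

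This needs no new data and no design change. The cost is one extra row per ORR table and a reported ORR that may look slightly less favourable. The difference in CI level between protocol 9.4.2 and SAP 6.1 should be resolved as its own item; both rows should use the same level.
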